## 5 RANDOMIZATION

Subjects will be randomized to receive one of the treatments (SENS 29 mg dose, SENS 43.5 mg dose, Placebo) according to relevant randomization list (non-ancillary study sites and ancillary study sites). The randomization lists will be stratified according to the duration of the hearing loss ( $\geq 24$  hours or  $< 24$  hours) and the intake of oral corticosteroids (Yes, No). Two randomization lists using a 1:1:1 randomization ratio will be generated for the whole study, one for the French sites involved in the ancillary study and one for all the other sites globally, including French sites not participating in the ancillary study. These two randomization lists will cover both Parts 1 and 2 of the study.

During Part 1, the 3 treatment arms will be allocated by the IWRS. After dose selection at the end of Part 1, only the placebo and the selected active dose (43.5 mg or 29 mg) will be allocated by the IWRS during Part 2.

	Sponsor:	Sensorion
	Protocol Number:	SENS 401-201
STATISTICAL ANALYSIS PLAN. PHASE 2-3-4		

The randomization lists will be generated centrally, and the investigator, the sponsor study team, the CRO and subjects will be blinded to the Investigational drug administration.

Pharmacokinetic parameters that could potentially unblind the study team will not be disclosed during the conduct of the study.

Investigators will have no access to the randomization code except under special circumstances. In case of an emergency, when knowledge of the randomization status is deemed necessary for the medical care of the patient, the randomization code can be unblinded for a specific patient (see section 11.3.4 of protocol).

A patient cannot be randomized more than once during the study.

A patient will be considered randomized when the IWRS has given the treatment number to be allocated.

## **6 PLANNED ANALYSES**

No statistical analysis plan (SAP) prepared in advance of the data can be absolutely definitive and the final Clinical Study Report (CSR) may contain additional tables or statistical tests if warranted by the data obtained. The justification for any such additional analyses will be fully documented in the final CSR.

The analysis of Part 1 will include only patients of Part 1. Meanwhile, the analysis of Part 2 will include only patients of Part 2.

### **6.1 Analysis Sets**

Subjects excluded from the analysis sets and the reason for their exclusion will be listed in Appendix 16.2 of the CSR.

#### **6.1.1 Intent-To-Treat Analysis Set**

The Intent-to-Treat (ITT) analysis set will comprise all randomized patients according to randomization group. All efficacy analyses will be performed on the ITT analysis set.

#### **6.1.2 Per-Protocol Analysis Set**

The Per-Protocol (PP) analysis set will comprise all patients of the ITT analysis set without major protocol deviation, which could affect the analysis of the primary efficacy endpoint. Selected

	Sponsor:	Sensorion
	Protocol Number:	SENS 401-201
STATISTICAL ANALYSIS PLAN. PHASE 2-3-4		

efficacy analyses (primary efficacy endpoint and secondary endpoints) will be repeated on the PP analysis set.

All protocol deviations will be assessed and documented on a case-by-case basis before the database lock, and deviations considered to have a serious impact on the efficacy results will lead to the relevant subject being excluded from the PP analysis set. Before the soft database lock, that is, when all subjects have completed (or prematurely discontinued) the 4 week treatment period, potential subject exclusions from the PP analysis set will be reviewed by the Sponsor and documented in a subject evaluability document.

### **6.1.3 Safety Analysis Set**

The Safety analysis set will comprise all treated patients. Subjects will be analyzed based on the treatment actually received. In the situation of accidental dispensation of two or three distinct treatments to the same patient, the patient will be counted for the whole study on the highest dose received.

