### **Analysis sets**

- The intent-to-treat (ITT) analysis set will comprise all randomised patients according to randomisation group. All efficacy analyses will be performed on the ITT analysis set.
- The per-protocol (PP) analysis set will comprise all patients of the ITT analysis set without major protocol deviation. Selected efficacy analyses (primary efficacy endpoint, secondary endpoints) will be repeated on the PP analysis set.
- The safety analysis set will comprise all treated patients according to treatment received.

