#### 9.5 Packaging and labeling

SENS-401 and matching placebo will be inserted in bottles with a child resistant cap. The bottles are packaged and labeled into a sealed clinical pack that includes 3 bottles including 30 tablets each of the investigational product or placebo for a 14-day administration including 1 additional day (rescue tablets). Twice daily, each patient will take 3 tablets (one tablet from each of the 3 bottles) included in one assigned pack. Each patient will receive 2 clinical packs (inserted into a final pack) according to the randomisation lists. During the 28-day treatment period, in exceptional case of any bottle being lost, the IWRS can allocate a replacement treatment number to a patient. The first dose to be administered at the study site will be taken out from one of the clinical packs that will be dispensed to the patient on Day 1 (visit 2), to be taken home. The content of the labeling is in accordance with the local regulatory specifications and requirements.

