#### **13.3.2 Safety population**

The safety analysis set will comprise all treated patients according to first treatment actually received.

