## 6.9 Prior and Concomitant Medications

For each part of the study, separate tabulations will be produced for prior and concomitant medications presented by randomized treatment group and overall, for the Safety analysis set. Prior medications are defined as all medications that started and stopped before the date of first dose of study drug. Concomitant medications are defined as medications that started prior to, on or after the date of first dose of study drug and ended on or after the date of first dose of study drug or are ongoing at end of study. Prior and concomitant medications will be summarized using Anatomic Therapeutic Chemical (ATC) Level 2. All medications will be coded using the most recent version of the WHO Drug Dictionary available at the time of database lock.

A separate tabulation for study treatment concomitant medications, defined as medications that started before date of the first dose of study drug and continued while on study drug or medications that started between the day of the first dose of study drug (included) and the date of the last dose of study drug (included) will be displayed by randomized treatment group and overall, for the Safety analysis set.

A separate tabulation for prior and concomitant use of oral corticosteroids (excluding use as rescue medication) will be displayed by randomized treatment group and overall, for the Safety analysis set.

A separate tabulation for concomitant corticosteroid as rescue treatment will be tabulated. Supporting dosing information will be listed, along with the other prior and concomitant medications.

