## 6.10 Exposure to Study Drug

Extent of exposure (number of days of exposure to study drug) will be presented by randomized treatment group for the Safety analysis set.

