### 6.14 Safety Analyses

The safety analyses will be presented by the treatment actually received for the Safety analysis set. In the situation of accidental dispensation of two or three distinct treatments to the same patient, the patient will be counted for the whole study on the highest dose received.

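### SAP 6.9 and 6.10 group medications and exposure on the Safety set by randomised arm while 6.14 groups adverse events by treatment received, and the SAP departs without declaration from the protocol's rule for a patient given more than one treatment

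*SAP*

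**What the plan says.** **Who belongs to which safety arm.** Protocol 13.3.2: "The safety analysis set will comprise all treated patients according to first treatment actually received". The protocol synopsis, under Analysis sets, is looser: "The safety analysis set will comprise all treated patients according to treatment received". It has no rule for a patient who took more than one treatment. SAP 6.1.3 also starts from treatment actually received, but where two or three treatments were dispensed by accident, "the patient will be counted for the whole study on the highest dose received". SAP 6.14 repeats that rule.

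**How Safety-set tables are grouped.** SAP 6.14: "The safety analyses will be presented by the treatment actually received for the Safety analysis set". SAP 6.10: "Extent of exposure (number of days of exposure to study drug) will be presented by randomized treatment group for the Safety analysis set". SAP 6.9 has its medication tables "presented by randomized treatment group and overall, for the Safety analysis set". SAP 6.11 summarises compliance on the Safety set by treatment group, without saying whether randomised or received.

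**Declared changes.** SAP section 8 lists ten changes to the protocol's analysis. One of them alters a safety definition (the time window for treatment-emergent events). The highest-dose rule is not listed.

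**The concern.** Exposure and adverse event tables are read together: a reader looks at how long an arm was on drug and then at what happened in it. That works only if both tables place each patient in the same arm. Here a patient randomised to placebo who in fact received active drug has the exposure and co-medication reported under placebo and the adverse events under active drug, or the reverse for the opposite error. Nothing on the page would reveal this. The output list titles the adverse event, exposure, compliance and medication tables alike as Safety Analysis Set, and SAP 6.3 gives one set of arm labels for all of them.

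The second issue is which arm a patient with more than one treatment belongs to. The protocol body and the SAP give different answers, and a reader who relied on section 8 for departures from the protocol would not know that the rule had changed.

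**Working it through.** The documents state no figure on this point, so the check sets the rules side by side and then sizes the effect of one patient. The only numerical inputs are 37 patients per arm in Part 1 (Protocol 7.5) and 28 days of treatment (Protocol 9.1).

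**Step 1. Grouping used on the Safety set**

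| Table | SAP section | Grouping |
|---|---|---|
| Adverse events and other safety data | 6.14 | Treatment actually received |
| Exposure | 6.10 | Randomised |
| Prior and concomitant medications | 6.9 | Randomised |
| Compliance | 6.11 | Not stated |

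Compliance divides tablets taken by a multiple of the extent of exposure, so its grouping should at least be explicit.

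**Step 2. One patient given the wrong treatment throughout.** Assume 37 treated per arm, 28 days each, and one patient randomised to placebo who received only 43.5 mg. The multiple-treatment rule is not needed here.

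- Exposure table (randomised): placebo N = 37, 43.5 mg N = 37, each with 37 × 28 = 1,036 patient-days.
- Adverse event table (received): placebo N = 36, 43.5 mg N = 38.
- Days actually taken by those arms: placebo 36 × 28 = 1,008; 43.5 mg 38 × 28 = 1,064.
- The exposure table understates 43.5 mg by 28 days (28/1,064 = 2.6%) and overstates placebo by 28 days (28/1,008 = 2.8%).

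**Step 3. Does this distort adverse event incidence?** No. SAP 6.14.1 plans subject incidence and event counts, and SAP 6.3 bases percentages on subjects or non-missing observations. A patient placed in the 43.5 mg arm is counted there in both numerator and denominator. No exposure-adjusted rate is planned, so exposure days are not the denominator of any adverse event table.

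**Step 4. When do the two multiple-treatment rules disagree?** Order the treatments placebo (P) < 29 mg (L) < 43.5 mg (H).

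| Order received | Protocol 13.3.2 (first) | SAP 6.1.3 (highest) | Same arm? |
|---|---|---|---|
| P, L | P | L | no |
| P, H | P | H | no |
| L, H | L | H | no |
| L, P | L | L | yes |
| H, P | H | H | yes |
| H, L | H | H | yes |

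The rules differ in 3 of 6 orders. With all three treatments they differ in 4 of 6 (every order that does not start with H). In general they differ exactly when the first treatment was not the highest dose.

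**Step 5. Size of the rule difference.** Take one patient who took placebo and then 43.5 mg and had one event, with 37 per arm otherwise correctly treated and no other such event.

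- Protocol rule: placebo 1/37 = 2.7%, 43.5 mg 0/37 = 0%. Active minus placebo = −2.7 points.
- SAP rule: placebo 0/36 = 0%, 43.5 mg 1/38 = 2.6%. Active minus placebo = +2.6 points.

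Under SAP 6.10 this patient's exposure stays in the randomised arm whichever rule is used. SAP 6.2.8 computes exposure as one span from first to last dose, so the days are not split by treatment either.

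**The case against.** The case for leaving the text alone is reasonable. Treatment is allocated centrally, so errors should be rare. Protocol 9.5 says that "the IWRS can allocate a replacement treatment number to a patient", but only exceptionally, when a bottle is lost, and nothing suggests that the replacement comes from another arm. Counting a patient on the highest dose is a cautious choice for safety. The protocol's statistical section describes itself as an outline to be completed by the SAP, and the synopsis wording is compatible with SAP 6.1.3.

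Most of this stands, and it limits the size of the point. It does not remove it. The SAP itself foresees accidental dispensation of two or three treatments, so its tables should handle that case consistently. Caution in assigning events is also no reason to leave the same patient's exposure in another arm.

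A reader might infer three stronger things that the documents do not support:

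- **That events are divided by the wrong arm's denominator.** Step 3 shows that they are not.
- **That dose selection is compromised.** SAP section 1 says the analyses conducted for the Data Monitoring Committee follow a separate plan, which is not among the documents. Nothing shows that the rule in 6.1.3 governs that committee's tables.
- **That the protocol's first-treatment rule is the correct one.** Each rule misattributes something. Highest dose credits active drug with events that preceded any active dose. First treatment credits placebo with events that followed a later active dose. Which error is larger depends on the day of the change.

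**Conclusion.** The point holds as a consistency defect of small size. On one Safety set, the SAP places exposure and medications by randomised arm and adverse events by treatment received. For a patient whose two arms differ, those tables have different Ns and different patients, and exposure cannot be read as the time at risk behind an arm's events. This covers any such patient, including one given a single wrong treatment throughout.

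Separately, the protocol body and the SAP assign a patient to different arms whenever the first treatment was not the highest dose, and section 8 is silent on it.

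The number of patients affected is not given and may be zero. The figures in the working assume 37 treated per arm and exactly one affected patient, and those in Step 5 apply only if that patient had the event in question. Efficacy analyses on the ITT set are untouched.

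**What to change.** 1. In SAP 6.9, 6.10 and 6.11, present the Safety-set tables by treatment actually received, using the same assignment rule as 6.1.3 and 6.14. State the grouping in the table titles or footnotes.
2. Reconcile Protocol 13.3.2 with SAP 6.1.3 and 6.14, or list the highest-dose rule in SAP section 8 as a change from the protocol. Either rule can be defended; it must be one rule, and declared.
3. For any patient who received more than one treatment, list adverse events by onset relative to the change of treatment. This shows what either rule hides, and it also covers the unsplit exposure span in SAP 6.2.8.

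The cost is wording in a few SAP sections, one line in section 8 and one short listing, which may be empty. No new data, sample size or efficacy analysis is involved.

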## **6.2 Derived Data**

This section describes the derivations required for statistical analysis. Unless otherwise stated, variables derived in the source data will not be re-calculated.

### **6.2.1 Race**

Where more than one race category has been selected for a subject, these race categories will be combined into a single category labeled “Multiple” in the summary tables. The listings will reflect the original selected categories.

### **6.2.2 Baseline**

Baseline for efficacy is defined as the last non-missing value (either scheduled, unscheduled or repeat) up to the randomization day included but before randomization date and time. According to the protocol, no data are expected to be collected between the randomization and the first intake of study drug.

Baseline for safety is defined as the last non-missing value (either scheduled, unscheduled or repeat) up to the date of first dose of study drug.

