## 7 STUDY DESIGN

### 7.1 Description of the protocol

This is a double-blind, randomised, placebo-controlled, international study. The study will assess the efficacy and safety of orally administered SENS-401 in patients suffering from sudden sensorineural hearing loss (SSNHL).

Patients will be included if they are presenting with sudden hearing loss with onset 96 hours or less, ago. Based on inclusion/exclusion criteria, most patients will present with idiopathic or noise induced SSNHL. The screening evaluation including ear examination with otoscopic and tympanometric examination, will confirm the diagnosis and no exclusion criteria from past medical/surgical or otologic history, concomitant treatments, laboratory tests or other concomitant diseases. The duration of the disease will be calculated from the reporting time onset of hearing loss. Eligible patients will undergo evaluations including audiometric tests (pure tone audiometry) to confirm the eligibility.

Patients will be randomised to receive one of the treatments according to the relevant randomisation list (non-ancillary study sites and ancillary study sites) . Audiometric tests, speech audiometry, numerical rating scales and questionnaires will be also performed before the first intake of the investigational drug at the investigational site. The randomisation will be further stratified according to the duration of the hearing loss ( $\geq 24$ hours, or  $< 24$  hours) and the intake of corticosteroids.

Patients will be requested to attend 4 additional visits when otologic examination and audiometric tests and speech audiometry will be performed on day 7( $\pm 2$ ) and 14 ( $\pm 2$ ), at the end of treatment visit on day 28( $\pm 3$ ), and at the follow-up visit (the end of the study visit) on Day 84 ( $\pm 3$ ).

Patients will be followed for adverse events throughout the study. Inquiry about potential untoward events will be done at every on-site visit.

Safety parameters will include routine blood tests (complete blood count, chemistry, liver function tests and lipid profile), pregnancy tests (if applicable), cardiac evaluation by ECG, physical exams including neurological, otologic examination, tympanometry and vital signs (blood pressure, heart rate and body temperature).

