### 10.1 Efficacy assessments

#### 10.1.1 Pure Tone Audiometry

Pure tone audiometry is considered the diagnostic gold standard for assessing SSNHL (11) (24). The primary purpose of pure tone audiometry is to determine the degree, type and configuration of hearing loss as its measurement covers the entire auditory pathway from the external ear to the cortex.

It is a standardized subjective hearing test in which air and bone-conduction hearing thresholds in decibels (dB) for a set of fixed frequencies between 0.25 kHz and 8 kHz are plotted on an audiogram for each ear independently.

Audiometry will be performed in order to determine the pure-tone air-conduction and bone-conduction thresholds for each ear according to the recommended procedure of the British Society of Audiology and the guidelines of the American Speech Language Hearing Association (ASHA).

The detailed procedures will be described in a specific manual. All materials will need to be calibrated before the study start and on a monthly basis, following ASHA, American Association of Audiology (AAA), American National Standards Institute (ANSI) recommendations and military standards where applicable (6), (7), (8), (9).

At the inclusion visit, pure-tone air-conduction testing should be immediately repeated at 1 and 2 kHz to determine that the subject provides reliable responses. Responses are considered reliable if retest thresholds at both frequencies do not exceed  $\pm 5$ dB of the previously obtained threshold response.

Pure tone air and bone conduction thresholds will be determined for each ear (best ear at first) at 0.25, 0.5, 1, 2, 3, 4, 6, and 8 kHz for air conduction and 0.5, 1, 2, 3, 4 kHz for bone conduction using the descending method of limits (modified Hughson Westlake procedure as follows: initial descent towards threshold is accomplished in 10-dB steps. Beginning with the first non-response, level is increased by 5-dB for each non-response and decreased by 10-dB after each correct detection response.

The baseline pure tone audiometry test is the last test performed at site within 24 hours prior to the first study drug administration. In case of longer time or if a pure tone audiometry test was performed elsewhere than at study site, the test should be repeated prior to the first study drug intake. If a screening test has been performed at the study site within 24 hours prior to the first study drug intake, there is no need to repeat it.

---

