### 10.2.4 Electrocardiogram (ECG)

A standard digitalized 12-lead electrocardiogram (ECG) will be performed at baseline (Visit 2) prior to randomisation, on Day 7 (Visit 3), Day 14 (Visit 4), and End of treatment visit Day 28 (Visit 5). Each ECG will be triplicated. Ideally at V4 and V5 least one of the PK samples MUST be collected within 15 minutes of the 3rd ECG test being performed.

Heart rate will be recorded from the ventricular rate and the PR, QRS and QTc ( $QTc = QT / [60 / \text{heart rate}]^{1/2}$ ) intervals will be recorded. The digitalized ECG, collected in triplicate, will be managed with a central reading. Corrections of the QT interval will be calculated using Fridericia's and Bazett's formula. Changes from the baseline QT interval will also be assessed.

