### **11.1.2 Baseline visit - Visit 2 (Day 1)**

The following tests and procedures will be performed:

- Re-confirmation of eligibility by reviewing inclusion/exclusion criteria
- Checking for Concomitant medication
- Inquiring about adverse event and fill an adverse event form if any
- Recording of concomitant medication including oral corticosteroid use for SSNHL
- Vital signs: blood pressure and heart rate, temperature
- 12-lead digitalised ECG
- Otologic examination and tympanometry\*
- Audiometric tests: pure tone audiometry\*, OAE tests (optional)
- Word and speech recognition Tests
- Serum sample for Prestin concentration (before study drug intake)

The patient will be asked to complete specific questionnaires:

- Tinnitus and Vertigo presence and severity (NRS)
- QoL: EQ-5D-5L;
- TFI
- C-SSRS

\*Pure tone audiometry should be performed within the last 24 hours before the first study drug intake. In case of longer time or not performed at the study site, the Pure tone audiometry should be repeated. If a Pure tone audiometry was performed at the study site for screening less than 24 hours before the first study drug intake, there is no need to repeat it.

After all assessments have been completed, the investigator will connect to the IWRS for allocation of a randomised treatment kit number. The investigator will dispense to the subject the corresponding study drug that is to be taken at the site, immediately after all baseline assessments are performed. Patient should be instructed to take 3 tablets (one from each bottle of one clinical pack). Date and time of the intake should be recorded on the patient diary and e-CRF.

The patient will be given the treatment carton to be taken home and asked to complete a patient diary for IP and corticosteroid compliance. The patient will be instructed to return his/her treatment carton and diary at the following visit.

---

The patient will also be asked to record tinnitus presence and intensity in the SSNHL affected ear on a daily basis in the patient diary. He will be asked to return the diary at the following visit.

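### The safety baseline in SAP 6.2.2 stops at the date of first dose, not its time, so a post-dose Day 1 value can become baseline

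*SAP*

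**What the plan says.** SAP 6.2.2 gives two baselines. For safety it is the "last non-missing value (either scheduled, unscheduled or repeat) up to the date of first dose of study drug". For efficacy it is the last non-missing value "up to the randomization day included but before randomization date and time", and the SAP adds a reason: "According to the protocol, no data are expected to be collected between the randomization and the first intake of study drug".

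Protocol 11.1.2 sets the order at Visit 2: "After all assessments have been completed, the investigator will connect to the IWRS for allocation of a randomised treatment kit number". The investigator then dispenses drug "that is to be taken at the site, immediately after all baseline assessments are performed". Protocol 9.6 has the date and time of that first intake entered on the eCRF.

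For pure tone audiometry (PTA), Protocol 10.1.1 has its own definition: "The baseline pure tone audiometry test is the last test performed at site within 24 hours prior to the first study drug administration".

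The safety baseline feeds three kinds of output: changes from baseline, the marked vital-sign abnormalities of SAP 6.14.3 (which need both a level and a change from baseline), and the laboratory marked-abnormality percentages of SAP 6.14.2 (whose denominator leaves out subjects already meeting the criterion at baseline).

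**The concern.** The two sentences of SAP 6.2.2 are built differently. The efficacy sentence cuts off at a date and time; the safety sentence cuts off at a date alone. Because it also admits unscheduled and repeat values and takes the last of them, any value obtained after the on-site dose on Day 1 displaces the pre-dose value.

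Such values are foreseeable. Protocol 11.1.7 provides unscheduled visits for adverse events and abnormal values, and Protocol 11.1 and 12.6 ask for abnormal laboratory or ECG results to be rechecked at once. A patient measured again on Day 1 because something looked wrong after dosing is the one for whom the rule picks an on-drug value. This also sits badly with SAP 6.14.1, where an event with onset on or after first dose is treatment-emergent: the event would count as on treatment while the measurement documenting it served as the pre-treatment reference.

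**Working it through.** No figure in the plan depends on this rule, so the check is a reading of the text with one illustration.

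**1. What the safety rule selects.** A value taken after the dose on Day 1 carries the first-dose date, so it passes the cut-off. It is later than the Visit 2 value, so it is the last. It becomes baseline.

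**2. Effect on one patient.** The readings below are invented for illustration; the criterion (SBP at or below 95 mmHg with a fall of at least 20 mmHg) is from SAP 6.14.3.

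| Baseline used | Baseline SBP | Post-dose Day 1 SBP of 90 | Day 7 SBP of 122 |
|---|---|---|---|
| Last value before the dose | 125 | 90 − 125 = −35, meets the criterion | 122 − 125 = −3 |
| SAP 6.2.2 as written | 90 | is the baseline, not counted | 122 − 90 = +32 |

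Every later change is shifted by the pre-dose value minus the post-dose value, here 125 − 90 = 35 mmHg.

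**3. Effect on a group.** Assume one such patient in an arm where everyone contributes data. With 37 per arm in Part 1, the arm's mean change moves by 35/37 ≈ 0.9 mmHg and the abnormality percentage by 1/37 ≈ 2.7 points. With 95 per arm in Part 2 the figures are 35/95 ≈ 0.4 mmHg and 1/95 ≈ 1.1 points. The number of such patients is not in the documents; it could be zero.

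**4. Laboratory denominator.** Routine bloods are scheduled at Visits 1, 4 and 5 and not at Visit 2 (Protocol section 4 and 10.2.5). Baseline is therefore normally the screening sample, and any later blood result dated Day 1 replaces it. If a post-dose result meets a marked-abnormality criterion, SAP 6.14.2 treats the subject as abnormal at baseline and removes the subject from the at-risk set.

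**5. The other reading of the rule.** Taking the cut-off to exclude the first-dose date does not help. It would discard the Visit 2 pre-dose vital signs, and the C-SSRS, first collected at Visit 2, would have no baseline. The text needs a time.

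**6. Which data are exposed.** Mainly vital signs and bloods repeated after dosing on Day 1. The baseline ECG "will be performed at baseline (Visit 2) prior to randomisation", and SAP 6.2.11 leaves ECG analysis to a separate plan. Sample times are to be recorded for blood draws (Protocol 11.1); the documents do not say that vital signs are timed.

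**7. Efficacy baseline, by comparison.** Under the order in Protocol 11.1.2, the last value before randomisation and the last value before the dose are the same value. They part only if a test is done between IWRS allocation and dosing. Inclusion criteria 3.1 and 3.2 require audiometry no more than 24 hours before first treatment, and Protocol section 4 (footnote 5) and 10.1.1 require an older or off-site test to be repeated. What is left is textual: SAP 6.2.2 does not restate the on-site and 24-hour conditions for PTA, and the ten changes in SAP section 8 do not mention it.

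**The case against.** The strongest reply is that the gap has little room to act. No post-dose safety measurement is scheduled on Day 1; the next visit is Day 7. The safety analysis tests no hypothesis (Protocol 13.5.4). That stands, and it sets the severity.

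A reader might infer that the rule hides acute first-dose reactions. The documents do not support that. Onset on or after first dose makes an event treatment-emergent (SAP 6.14.1), a missing start time on the first-dose date is imputed to the dose time (SAP 6.2.5), medically meaningful laboratory or ECG abnormalities are reported as adverse events (Protocol 12.4.1), and vital signs and laboratory data are listed (SAP 10.1). The loss is confined to descriptive summaries. The telemetry finding in Protocol 5.3.3 of slightly lower blood pressure with modestly raised heart rate is non-clinical and unrelated to dose, and Protocol 5.3.4 reports good tolerability in 36 volunteers. It makes vital signs a relevant place to be exact, no more.

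A further reply is that correcting the baseline alone may not restore the illustrated event. SAP 6.2.16 applies its windows to all safety endpoints and the first opens on Day 5, so a Day 1 value may belong to no post-baseline visit. This also stands, and the fix has to address it.

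**Conclusion.** The safety sentence is a real wording gap of minor severity. It can misplace the baseline of any patient with a post-dose Day 1 vital sign or blood value, probably few patients. Alpha, power, sample size and the primary analysis are untouched. The conclusion assumes that the date cut-off is programmed as written, including the first-dose date.

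A reader might go further and infer that both baselines are anchored to the wrong moment, or that a stale or off-site screening audiogram would replace the protocol's baseline and leave patients without baselines for speech threshold, tinnitus or quality of life. That is not supported. Protocol 7.1 does say only that "numerical rating scales and questionnaires will be also performed before the first intake of the investigational drug at the investigational site", which is looser than 11.1.2, but it does not direct testing after randomisation, and the visit procedure puts all assessments before IWRS allocation. A pre-randomisation value is also a valid covariate for an intent-to-treat comparison. Those outcomes would need a departure from the visit order, and for audiometry also from the 24-hour eligibility rule. For efficacy, only the unlisted difference from Protocol 10.1.1 remains.

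**What to change.** In SAP 6.2.2:

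- Define the safety baseline as the last non-missing value before the date and time of first dose.
- For Day 1 records without a time, treat the scheduled Visit 1 or Visit 2 record as pre-dose and list untimed unscheduled Day 1 records separately. Calling them all post-dose would misclassify repeats made before the dose.

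In SAP 6.14.2 and 6.14.3, state that post-dose Day 1 values count in the any-post-baseline marked-abnormality tables, although they fall outside the visit windows of 6.2.16.

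For efficacy, keep the randomisation anchor. Add a cross-reference to Protocol 10.1.1 for PTA, flag patients whose baseline audiogram was not on site within 24 hours before first dose, and keep them in the ITT analysis; excluding them would leave randomised patients without a baseline for the primary model. List the difference in SAP section 8.

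The cost is a few sentences and a small programming change. The first-intake time is already collected, and no new data are needed.
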